### **Medication**

As described above, we will compare pill placebo to dexamethasone in a double-blind manner. Patients will be instructed to take the single pill the night before each VRE session and will be given a reminder call the night before the VRE session to reinforce medication compliance.

### **Patient Compliance**

Individual patient compliance with treatment will be evaluated based on attendance at therapy sessions, pill count, completion of assessments and cortisol levels present at onset of each therapy session.

## **7.0 Pathology**

Participants must meet DSM--V criteria for Posttraumatic Stress Disorder due to military service in Iraq or Afghanistan.

## **8.0 Patient Assessment**

### **Pre-Treatment Assessment**

Potential subjects will be asked to provide a copy of their DD214 to verify combat exposure. Once a potential participant has met all screening inclusion and exclusion criteria and consented to participate, the CAPS will be administered to determine current PTSD status.

The Clinician Administered PTSD Scale (CAPS-5; Blake et al., 1995; updated for DSM V) is an interviewer-administered diagnostic instrument that measures PTSD. The CAPS provides a diagnostic measure of PTSD and a continuous measure of the severity, frequency, and intensity of the three symptom clusters (intrusion, avoidance, and arousal) and overall PTSD. If positive for current PTSD on the CAPS, and all other eligibility criteria are fulfilled, the rest of the pre-treatment measures will be administered.

The Columbia–Suicide Severity Rating Scale. (Columbia; Posner et al., 2011). The Columbia–Suicide Severity Rating Scale was initially designed to assess suicidal ideation and behavior in clinical trials. It assesses occurrences, types, and severity of suicidal ideation and all types of behavior.

Neurobehavioral Symptom Inventory (NBI; Mererko et al., 2012). This is a 22 item measure designed to assess postconcussive symptoms following deployment-related mild traumatic brain injury among veterans.

Patient-Reported Outcomes Measurement Information System 8a and 4a -Satisfaction with Social Roles and Activities (PROMIS 4a, PROMIS8a, (Cella et al., 2010). The PROMIS item bank assesses satisfaction with performing one's usual social roles and activities.

The Patient Health Questionnaire (PHQ-9; Kroenke, Spitzer, & Williams 2001). The PHQ-9 is assesses each of the 9 DSM-IV criteria for depression as "0" (not at all) to "3" (nearly every day).

The Alcohol Use Disorders Identification Test—Consumption (AUDIT-C; Frank, Danielle et al. 2008). The AUDIT-C is a brief validated self-report screen for risky drinking and alcohol abuse and dependence (alcohol misuse). It has three questions that ask the frequency and amount of alcohol consumed.

Life Events Checklist for DSM-V (LEC-5; Weathers, et al., 2013). This is a self-report measure designed to screen for potentially traumatic events in a respondent's lifetime. It is useful in more specifically identifying the Criterion A stressor queried during the CAPS interview.

The Demographics Questionnaire covers demographics; family composition; personal psychiatric history; and income and education to obtain a *Hollingshead Four Factor Scale of Socioeconomic Status*.

The Childhood Trauma Questionnaire (CTQ; Bernstein, 1995) is a self-report measure which assesses history of childhood trauma employing a Likert-scale format with 5 responses per item.

PTSD Symptom Scale-Interview for DSM-5 (PSS-I-5; Foa & Capaldi, 2013) assesses current symptom frequency and intensity for the past month.

The MINI International Neuropsychiatric Interview (M.I.N.I. ; Sheehan, D. V. et al., 1998) will be administered to screen axis 1 disorders and to establish co-morbid diagnosis.

The Beck Depression Inventory-II (BDI; Beck, Steer, & Brown, 1996) is a 21-item measure of cognitive and vegetative symptoms of depression is widely used in a variety of populations, including trauma victims and is sensitive to treatment effects on depression.

State Trait Inventory (STAI; Spielberger et al., 1983). The STAI-State is a 20-item self-report scale employing a Likert scale format with 4 responses per item (1-4). Ten of the STAI items measure feelings of stress and anxiety, while the remaining ten items measure feelings of relaxation.

Deployment Risk and Resiliency Inventory (DRRI; King et al., National Center for PTSD, 2003) is a self-report measure of pre-deployment, deployment and post-deployment experiences and trauma specific to the veteran population. The scale employs yes-no and Likert scale format responses ranging from 1-5.

The Quality of Life Inventory (QOLI; Frisch et al., 1992) The QOLI consists of 16 items selected to include all areas of life that have been empirically associated with life satisfaction. Respondents rate how important each of the 16 domains is to their overall satisfaction and happiness; they then rate how satisfied they are in the area. The total score reflects one's satisfaction in areas that one considers important to them. The QOLI's sensitivity to treatment-related change has been demonstrated with clinical samples of depressed, socially anxious/phobic, and chemically-dependent patients.

Clinical Global Impressions Scale, Severity of Illness (CGI-Severity; Guy & Bonato, 1970). This is a study personnel rated measure of severity of illness ranging from 0 (not assessed) to 7 (among the most extremely ill patients).

Mini-Mental State Examination (MMSE; Folstein et al., 1975). The MMSE is an 11-question, personnel rated measure that covers patient orientation, registration, attention/calculation, recall, and language skills.

Psychophysiological Patient Report: This is a brief self-report administered following each psychophysiological assessment. Using a likert scale (Not at all to Very/Severe) participants rate the assessment VE as to 1. How closely the video matched their experience and 2. How distressing they found the video.

Intent to Attend (Leon et al., 2007) is a short, two question survey asking participants how likely they are to complete all of the study and how likely they are to attend the next session.

Psychophysiological Reactivity Assessment: Acoustic startle response, skin conductance, and heart rate will be assessed during a viewing of three VR scenes. The VR scenes will be presented through a head-mount display for a duration of 15 minutes. Psychophysiological data collection is described below.

Cortisol Reactivity Assessment: Saliva cortisol will be sampled at four intervals relative to the 15-min viewing of VR scenes: prior to, immediately after, 15 min, and 45 min after VR. Cortisol sampling methods are described below.

The Emory Treatment Resistance Interview for PTSD (E-TRIP) is a structured interview that assesses prior trials of pharmacology and psychotherapy PTSD treatments and provides a quantitative indicator of PTSD treatment resistance.

Posttraumatic Stress Disorder Checklist (PCL): The PCL is a 17-item self-report checklist of PTSD symptoms based closely on the DSM-IV criteria. Respondents rate each item

from 1 ("not at all") to 5 ("extremely") to indicate the degree to which they have been bothered by that particular symptom over the past month.

#### Measures at each Therapy Session

Expectancy of Therapeutic Outcome Questionnaire (ETOQ) assesses how logical the treatment appears, and the expectancy of success for the patient and for others. This measure is administered after session 1 only.

Clinical Global Impressions Scale, Severity of Illness (CGI-Severity; Guy & Bonato, 1970). This is a study personnel rated measure of severity of illness ranging from 0 (not assessed) to 7 (among the most extremely ill patients). This measure is administered after sessions 1–6.

Clinical Global Impression – Improvement (CGI-Improvement; Guy & Bonato, 1970). This is a study personnel rated measure of patient's improvement since start of study ranging from 1 (very much improved) to 7 (very much worse). This measure is administered after sessions 2-6.

Clinical Global Improvement Scale, Patient Report (CGI - Self Report; Guy & Bonato, 1970). This is a self-reported global measure of change in severity of symptoms, ranging from 1 (*very much improved*) to 4 (*unchanged*) to 7 (*very much worse*). This measure is administered after sessions 1-6.

The PTSD Symptom Scale is a 17-item interview used to aid in the detection and diagnosis of PTSD (described above), administered before sessions 2-6.

Subjective Units of Discomfort (SUDs) will be gathered during each exposure session (sessions 2-6). Participants will be asked to rate their level of discomfort on a scale of 0 (no anxiety) to 100 (panic levels of anxiety) every 5 minutes during the VR exposure.

Intent to Attend (Leon et al., 2007) is a short, two question survey asking participants how likely they are to complete all of the study and how likely they are to attend the next session.

Blinded Medication Check is a one-question measure to assess which medication the participant believes they took.

Cortisol Sampling will be obtained from saliva in order to measure post-dexamethasone cortisol levels and detect the presence of dexamethasone in saliva. Cortisol sampling methods are described below.

#### Post treatment and 3, 6 and 12-month Follow-up Assessments

The Clinician Administered PTSD Scale (CAPS) (see above).

The Beck Depression Inventory (BDI) as above.

The PTSD Symptom Scale as above.

The Clinical Global Improvement Scale (Severity, Improvement, and Patient Report) as described above.

The Quality of Life Inventory as above.

The State Trait Inventory as above.

Patient Update Interview: This a brief study personnel-interview administered to obtain general patient follow-up data, i.e. between-assessment treatment, medication changes, substance use status/changes, and patient report on relationship/employment/health changes.

Psychophysiological Patient Report as above.

Psychophysiological and Cortisol Reactivity (as described above) to the VR scenes will be assessed at each follow-up point.

Posttraumatic Stress Disorder Checklist (PCL) as above.

### Psychophysiological Data Collection:

Psychophysiological data will be acquired at a sampling rate of 1kHz, amplified and digitized using the EMG module of the Biopac MP150 for Windows (Biopac Systems, Inc., Aero Camino, CA).

1. The acoustic startle response (eyeblick component) will be measured via electromyographic (EMG) recordings of the right *orbicularis oculi* muscle. Two 5 mm Ag/AgCl pre-gelled disposable electrodes will be positioned approximately 1 cm under the pupil and 1 cm below the lateral canthus. The startle probe (noise burst) will be a 108-dB (A) SPL, 40-ms burst of broadband noise with a near instantaneous rise time.
2. Skin conductance level and skin conductance response will be acquired at a sampling rate of 1 kHz using the GSR module of the Biopac system. Two 5 mm Ag/AgCl disposable electrodes filled with isotonic paste will be attached to middle phalanges of the second and fourth finger of the non-dominant hand.
3. Heart-rate and heart-rate variability (HRV) will be measured using the ECG module of the Biopac system at a sampling rate of 1 kHz. One 5mm Ag/AgCl electrode will be placed on the chest above the right clavicle, another electrode will be placed on the chest under the left side of the ribcage.

### Collection of Salivary Samples:

Salivary samples will be collected in prior to the beginning of the VR assessment, immediately after viewing VR scenes and 15 and 45 min after VR scenes using saliva collection tubes. The saliva samples will be assayed for cortisol levels on assessment days. On intervention days, saliva samples will be collected in the morning when the patient arrives for the session and will be assayed for cortisol and presence of dexamethasone to confirm compliance. Assays will be completed in the Yerkes Endocrinology Core Laboratory at Emory using commercial radioimmunoassay kits (DiaSorin, Stillwater, Minn.). The inter- and intra-assay coefficients of variation will be determined and is expected to be between 4-7%. Radioimmunoassay kits from IgG Corporation (Nashville, Tenn.) will be used to determine dexamethasone concentrations to confirm that subjects have detectable dexamethasone levels for the post-dex cortisol sample.

### Interventions:

VRE. The VRE treatment program will consist of 90-minute individual treatment sessions. Procedures include education about common reactions to trauma, breathing retraining, prolonged (repeated) virtual exposure to trauma, and discussion of thoughts and feelings related to exposure exercises. The discussion addresses unrealistic beliefs about the self and the world, attempting to “process” material that came up during the exposure and make new associations explicit (e.g., “You see, by staying with the image long enough, your anxiety decreases.”) Session 1 is devoted to information gathering, education about common reactions to trauma, elaboration of the index trauma, breathing retraining, and fostering a therapeutic alliance. The remaining 5-10 sessions consist of VRE interventions and discussion of these experiences.

The patient will be encouraged to expose him or herself to traumatic memories triggered by the virtual environments, following guidelines for standard exposure therapy. As the number of sessions is limited, we are limiting exposure to the identified index trauma, and in some cases, a second traumatic event. The therapist asks the patient to give a SUDs (Subjective Units of Discomfort, 0= no anxiety and 100=maximum anxiety) rating approximately every five

minutes during all exposures as an indication of his level of anxiety. The therapist makes appropriate comments and encourages continued exposure until anxiety has decreased. The therapist simultaneously views on a video monitor all of the virtual environments in which patients are interacting and therefore is able to comment appropriately and is attempting to match stimuli that the patient is describing to the virtual stimuli, as much as possible, for example by landing the helicopter at the appropriate time in the memory, or by having gunfire, bombs, fog, or night time to match the memory. The 90-minute session will consist of 15 minutes of checking in with the patient about their functioning and anxiety since the last session, up to 45 minutes of exposure to their traumatic memories and the virtual stimuli, followed by processing and discussion about the material from the exposure. Information is gathered each session on any other exposure the patient may have conducted, although no homework will be assigned, as patients will only be on study medication for office visits.

Medication. Beginning with session 2 (the first session where VRE is used), the patients will take either the dexamethasone medication (0.5 mg) or placebo 8-10 hours prior to the VRE session. A study staff member will call the patient to remind them to take their medication at the appropriate time. As the study will be double-blind, neither the patients, the study staff nor clinicians will know which pill the patient took. However, as a check for compliance, saliva samples will be tested for the presence of dexamethasone. These results will be available to investigators once the study is completed and unblinded. This approach has been used in our previous IRB protocols (IRB #51911, PI: [name]), with high compliance rates.

### **8.1 Procedure**

Study staff will conduct extensive phone screening to determine appropriateness of this project for each patient and will provide information on project design and procedures. Upon medical history review and a physical exam performed by the study physician, a pre-assessment visit will be scheduled at which time patients will be thoroughly evaluated as to inclusion and exclusion criteria (detailed above) and explained the procedures of the project in detail. Informed consent will be obtained at this pre-assessment visit. The consent form, CAPS and M.I.N.I. will be completed prior to official study entry. If eligible and willing to participate, individuals will officially be enrolled in the study and will complete the pre-treatment assessment questionnaires. During the pre-assessment visit we will collect a one-time saliva sample to be used for the purpose of DNA extraction. DNA extraction is optional and will be presented to participants under a separate consent. Following consent, initial diagnostic interviews, self-reports, and DNA extraction (if consented), psychophysiological data will be collected (described above), including 3 cortisol samples at each assessment, and the first of the therapy visits will be scheduled. Following randomization, the participant will receive a pill and be instructed to take it at 11pm before every VRE therapy session. During any visit after taking dexamethasone, the participants will be assessed for adverse effects of the drug by the study staff. Significant adverse effects will be reviewed by the study physician; if the study physician determines that the study puts the participant at undue risk, their participation will be stopped.

All treatment will be free of charge to the participant and no funding is available to compensate for these visits (treatment sessions 1-6 or 11). Post treatment and follow-up visits, however, (post, 3, 6, and 12-month follow-up) will be compensated \$20 for time and travel.

If the treating therapist makes a clinical judgment at the conclusion of treatment sessions that a participant requires additional follow-up treatment sessions for stabilization, these may be offered as compassionate care. The participant will also continue with scheduled post-treatment assessments as per the study protocol.

Independent Assessor Reliability Monitoring. All MINI and CAPS interviews will be videotaped and rated for reliability. Ten percent of the baseline MINI and CAPS interviews will

be randomly selected in an ongoing way in order to monitor the reliability of the interview process.

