## **1. Significance of the Proposed Research**

This type of combined treatment -- specific pharmacotherapeutic augmentation of psychotherapy -- would be novel and would potentially be generalizable to many different forms of psychotherapy for a wide range of disorders. If this translational research is successful, the ability of a relatively benign agent administered before a psychotherapy session to facilitate the psychotherapeutic process could have important clinical, humanitarian, and economic advantages. Although exposure therapy is highly effective in treating PTSD in those patients who complete the full regiment, it is sometimes difficult for patients to overcome the initially aversive component of imaginal or virtual exposure. In addition to enhancing the therapeutic effect of exposure therapy, we expect that reducing fear prior to the onset of the therapy session will make recalling traumatic memories more tolerable for the patients, resulting in fewer drop-outs and better compliance with therapy. This could have profound effects on improving patients' long-term outcomes.

Understanding the neurobiological underpinnings of PTSD is crucial to improving both psychotherapy and pharmacotherapy for these patients. Discovering brain-based phenotypic biomarkers of the disorder will optimize diagnosis and treatment strategy resulting in better and faster treatment response. These new strategies will be invaluable as the number of patients increases. There is no question that PTSD is a serious and urgent public health problem and that the biological mechanisms of vulnerability to developing psychopathology after trauma must

be investigated very closely. A promising candidate neurobiological mechanism involves the neurocircuitry of fear, which, according to several lines of evidence, appears to be dysregulated in PTSD ([name], et al., 2009; Liberzon & Martis, 2006; Milad et al., 2009; Norrholm, et al., 2011; Shin, et al., 2006).

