### **3.0 Participant Selection**

#### **3.1 Eligibility Criteria**

Participant Inclusion Criteria:

- (a) Participants will be 100 males and females between ages of 21 and 65.
- (b) Participants must meet DSM-V criteria for PTSD due to exposure to a trauma while serving in Operation Iraqi Freedom and/or Operation Enduring Freedom-Afghanistan and Operation New Dawn.

- (c) Patients must be literate in English.
- (d) Patients must be medically healthy or medically stable such that the stress of VR and DEX are not contraindicated. (e) Participants must comprehend his or her role in the study and the risks involved in order to be entered.

Gender and Minority Participants' Inclusion Plan. Males and females of all races and ethnic groups will be entered. The racial composition of Atlanta is 71% white, 26% black, and 3% other (based on the 1990 US Census). Approximately 1% of these persons are of Hispanic origins. The gender composition of Atlanta is 51% female. This study will provide free treatment and will be advertised in the popular press, thus ensuring equal opportunities for all to learn about and participate in this study. The treatment setting is located in a racially diverse county (DeKalb County), is easily accessible by public transportation and is wheelchair accessible. It is therefore expected that the study sample will closely approximate the demographic composition of Atlanta, except that only 15% of the military is currently female. Based on our current study of VRE, we expect that the current sample will be approximately 40% Caucasian, 60% non-caucasian, and 5% female. Persons between 18-21 will not be included, as there are specific treatments for children and younger people with PTSD and the effects of dexamethasone are unknown in children.

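### The adverse-effect check is worded as applying after dexamethasone and to effects of the drug; this conflicts with the blind and leaves VR exposure outside any adverse-event record, with no by-arm summary planned

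*Combined protocol and SAP*

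**What the plan says.** **The collection rule.** Section 8.1 (Procedure) states: "During any visit after taking dexamethasone, the participants will be assessed for adverse effects of the drug by the study staff". It continues: "Significant adverse effects will be reviewed by the study physician; if the study physician determines that the study puts the participant at undue risk", in which case participation ends. The rule for collecting refers to the drug; the rule for acting refers to the study.

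**The blind.** In Section 8.0, Interventions (Medication), "the patients will take either the dexamethasone medication (0.5 mg) or placebo" before each exposure session, and "As the study will be double-blind, neither the patients, the study staff nor clinicians will know which pill the patient took". Saliva is assayed for dexamethasone as a compliance check, but "These results will be available to investigators once the study is completed and unblinded".

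**VR as a stress.** An inclusion criterion in Section 3.1 reads: "Patients must be medically healthy or medically stable such that the stress of VR and DEX are not contraindicated". It names VR alongside the drug.

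**Where adverse events do not appear.** There is no adverse-event item among the measures at each therapy session, the post-treatment and follow-up measures, or the data sources in Section 9.0. The Columbia suicide scale is listed only before treatment. The arm comparisons in Section 10.2 cover symptom and psychophysiological measures, clinical response, number of sessions and dropouts.

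**The concern.** A harm rule in a blinded trial should be one that blinded staff can carry out identically in both arms. This one is triggered by a fact hidden from them and limited to effects they judge to come from the drug. Placebo control is what would allow that attribution to be made from data, by comparing event rates, and the plan does not use it for that purpose.

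The stake is the tolerability half of the rationale. The Significance section looks forward to "the ability of a relatively benign agent administered before a psychotherapy session to facilitate the psychotherapeutic process" and expects exposure to become easier to bear; Hypothesis 1 includes better tolerance of exposure therapy. Without an all-cause record by arm, the trial could report effects that staff ascribed to the drug, but not how often the same complaints arose on placebo. Reactions to the exposure, or to drug and exposure together, would have no defined place in the record.

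**Working it through.** **1. Can the rule be applied as worded?** Section 8.1 needs to know that dexamethasone was taken. Section 8.0 says "neither the patients, the study staff nor clinicians will know which pill the patient took", and assay results are withheld until unblinding. No permitted source tells staff which visits qualify, so the two sections conflict.

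**2. Read dexamethasone as the study pill.** The conflict goes and both arms are assessed. Four gaps remain:
- Scope: only effects of the drug count, so staff who do not know the arm must decide cause before recording.
- Exposure: a reaction put down to VR is outside the rule.
- Start: the 15-minute VR viewing at the pre-treatment assessment comes before randomisation and any pill, so it is not covered.
- Use: no form, item or by-arm summary is specified.

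**3. What else records harm in both arms?**
- Dropout (Section 10.1) includes serious adverse reactions and clinical complications, and Section 10.2 looks at dropout numbers by arm. But these are pooled with missed sessions. Because fewer dropouts are predicted with dexamethasone, better tolerance and added harm could offset each other in one count.
- SUDs and the CGI scales record anxiety during exposure and global change, including worsening. They are efficacy or process measures. The session list runs to session 6, while Section 6.0 allows 11; the Interventions text does extend SUDs to all exposures.
- The Psychophysiological Patient Report rates how distressing the VR scenes were, including before treatment.
- The Patient Update Interview covers health changes, but only from post-treatment onwards.

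None of these is an adverse-event record.

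**4. What would a by-arm comparison deliver?** The plan's 50 per arm (Section 10.2) is the input. It is close to reproducible: an exact two-sample t-test at d = 0.65, 85% power and two-sided 0.05 needs 44 per arm; 44/0.9 = 48.9, so 49 per arm and 98 in total, against the stated 100.

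The half-width of the 95% interval for a difference between two proportions near p, with n per arm, is 1.96 × √(2p(1−p)/n). The documents give no event rate, so p = 0.2 to 0.5 is an assumption.

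| n per arm | p = 0.2 | p = 0.5 |
|---|---|---|
| 50 | 1.96 × √(0.32/50) = 0.157 | 1.96 × √(0.50/50) = 0.196 |
| 45 (after the plan's 10% loss) | 1.96 × √(0.32/45) = 0.165 | 1.96 × √(0.50/45) = 0.207 |

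Power at 50 per arm, again under assumed rates, is about 38% for 5% v 15%, 51% for 10% v 25%, and 71% for 10% v 30%. No events of a given kind among 50 patients leaves a one-sided 95% upper limit of 1 − 0.05^(1/50) = 5.8%.

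**The case against.** The strongest reply is that Section 8.1 is loosely worded and nothing more. The sentence before the rule has the participant receiving a pill, and the rule itself speaks of the participants without separating arms. That reading is the natural one, and it stands.

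It also disposes of a tempting inference: that placebo patients, half the sample, get no adverse-effect assessment. To skip exactly that half, staff would have to know the arm, which the blind prevents.

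A reader might also infer that harm is never compared with placebo, or that harm from VR exposure is never recorded. The documents do not support either. Serious reactions and complications enter a dropout count that is looked at by arm, and SUDs, CGI, the distress rating and the Patient Update Interview record distress, worsening or health changes in all participants. Stopping also turns on risk from the study, not only the drug.

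Finally, this is a self-described pilot, the comparison would be imprecise, and enquiry as late as 12 months, long after the last pill, is partly a matter of preference. All fair. But these points limit the claim without answering the four gaps that remain after the wording is read generously.

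**Conclusion.** The point holds in a limited form. As worded, the rule in Section 8.1 conflicts with the blind in Section 8.0. Read as intended, it still makes blinded staff attribute cause before recording and leaves reactions to VR exposure outside the adverse-event record. No adverse-event item is listed at sessions or follow-up, and no by-arm comparison of adverse events is planned. Some harm-related information exists in both arms, but it is scattered across efficacy measures and a mixed dropout count.

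The size is that of a missing descriptive result: a risk difference known to about ±16 to ±20 points with 50 per arm, or about ±17 to ±21 after 10% loss, if event rates lie between 20% and 50%. Those rates are assumed. The efficacy analyses are not affected. This should be corrected, because it bears on a tolerability claim the trial itself makes and costs little.

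**What to change.** - **Section 8.1:** reconcile with Section 8.0 (Interventions) and Section 10.1. Reword so that every randomised participant, in both arms, receives the same short adverse-event enquiry at each scheduled session and assessment, whatever the suspected cause. Record relatedness to the pill and to VR exposure as two separate blinded judgements, made after the event is recorded. Record events at the pre-treatment VR assessment too, and show them separately because they precede randomisation.
- **Section 8.0:** add the item to the measures at each therapy session, for all sessions given, and to the post-treatment and follow-up list.
- **Section 10:** add a descriptive table of adverse events by randomised arm, with the denominator stated, risk differences and 95% intervals. Show dropouts due to serious reactions or complications separately from those due to missed sessions.

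No dose, visit schedule or stopping rule needs to change for this. The cost is some rewording, one short form at visits already planned, and one table. The downside is that more minor events will be recorded, and the comparison will remain descriptive.
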